8.6.2 Blood Samples for Incremental Recovery

In Arms 1 and 3 (PTPs), IR will be collected at Day 1 and at the closest visits after 10 EDs, after 50 EDs, and after 100 EDs, as outlined in [Table 8](#). Incremental recovery ($[\text{IU/mL}] / [\text{IU/kg}]$) is defined as FVIII activity (IU/mL) obtained 30 to 60 minutes following injection, per dose of (IU/kg) injection. Incremental recovery values will be baseline-corrected for pre-injection plasma FVIII activity.

If possible, subjects should have a 4-day washout from their last FVIII infusion before the IR samples are drawn. A pre-dose blood sample will be drawn. Subjects will then receive their prophylaxis dose of rVIII-SingleChain injection. For on-demand subjects, the usual dose used to treat a bleeding episode may be administered or any other dose determined by the investigator. A post-dose blood sample will be drawn 30 to 60 minutes (± 5 minutes) after the injection. The exact times of blood draws and the actual dose (IU/kg actual potency) administered will be recorded. Blood sample collection timepoints are presented in [Table 8](#).

Table 8: Blood sample collection timepoints for inhibitor and incremental recovery assessment (Arms 1 and 3 [PTPs])

	Day 1	Exposure days of rVIII-SingleChain ^A		
		10 EDs	50 EDs	100 EDs
Inhibitor ^B	From previous End of Study Visit	X	X	X
Incremental Recovery ^C	X	X	X	X

Abbreviations: CHO = Chinese hamster ovary; ED = exposure day; PTP = previously treated patient; rVIII = recombinant factor FVIII.

From “Guideline on the clinical investigation of recombinant and human plasma-derived factor VIII products” (EMA, 2011)

- A: For Arm 1, exposure days are cumulative from previous lead-in studies (calculated from the first dose of rVIII-SingleChain in any study). For Arm 3, exposure days will be calculated from the first dose of rVIII-SingleChain in the present study only.
- B: After 4-day washout period (if possible), inhibitor assessment will include inhibitors to FVIII, antibodies against rVIII-SingleChain, and antibodies against CHO proteins.
- C: After 4-day washout period (if possible), blood samples will be drawn: 1) prior to injection of rVIII-SingleChain, and 2) at 30 to 60 minutes (\pm 5 minutes) following injection. The exact times of blood draws post-injection will be recorded.

CCI

8.6.3 Blood Samples for FVIII Activity Level

In Arms 2 and 3, blood samples for FVIII activity level will be obtained at Screening if FVIII activity level is not available in the subject’s medical records. If FVIII activity level is determined at Screening, it must be determined at the local laboratory and the result must be available before enrollment.

8.7 Retention of Samples

In Arms 2 and 3, blood samples will be obtained at Visit 1 before the first dose of rVIII-SingleChain and at the End of Study Visit and retained for viral safety testing, if needed. For Arm 1, no additional Day 1 virology retention sample will be taken, but the sample from the End of Study Visit in the preceding study (ie, either CSL627_1001 or CSL627_3002) will be used as the Day 1 sample in the current study.

Retention samples will be stored by CSL for 5 years from the end of the study and will be analyzed only if there is a suspicion of a viral infection.

8.8 Prior and Concomitant Therapies

All drugs taken by a subject within 28 days prior to enrollment into the study are regarded as prior therapy and must be documented as such in the eCRF.

All drugs currently being taken by a subject at enrollment into the study, and which continue to be taken in addition to rVIII-SingleChain during the study, are regarded as concomitant therapy and must be documented as such in the eCRF.

Subjects should not be enrolled into the study if they receive any prohibited concomitant therapy or any concomitant therapy in a prohibited dosage that cannot be discontinued or reduced to a permitted level. Any IMPs other than rVIII-SingleChain are prohibited.

8.9 Assessment of Local Tolerability

8.9.1 Subject / Caregiver Assessment of Local Tolerability

In all study arms, local tolerability at the injection site will be assessed by the subject or the subject's caregiver after each rVIII-SingleChain injection administered by the subject or caregiver. Subjects (if capable) or the subject's caregiver will record in the subject diary a general judgment on the overall perception of the local reactions approximately 30 minutes after the end of the injection on a 5-point scale of none (0), very slight (1), slight (2), moderate (3), and severe (4). In addition, subjects will have the ability to record information in the diary regarding side effects.

8.9.2 Investigator Assessment of Local Tolerability (Arm 2 and Arm 3 Only)

In PUPs in Arm 2 and PTPs in Arm 3, the Investigator will perform an assessment of local tolerability at 30 ±10 minutes after each rVIII-SingleChain injection administered at the clinic.

If several injection sites are used, each site will be judged but only the site with the strongest reaction will be recorded, according to the following scales:

Erythema

Table 9: Erythema Rating Scale

Description	Score
None	0
Very slight (barely perceptible)	1
Well-defined	2
Moderate to severe	3
Severe (beet redness) to slight eschar formations (injuries in depth)	4

Edema or Induration

The size of any edema or induration will be determined by measuring the smallest and largest diameters.

Itching, Local Pain, or Local Heat

The severity of any local reactions of itching, local pain, or local heat will be assessed by questioning the subject based on the following classification: none (0), very slight (1), slight (2), moderate (3), and severe (4).

8.10 Visit Schedules

In all study arms, all subjects must provide written informed consent before any study-specific assessments or procedures are performed. Written informed consent is not required for assessments or procedures performed according to standard of care (eg, for diagnosis or treatment); results from such assessments may be used in the determination of study eligibility.

Written informed parental or guardian consent and assent of minors (if the subject is capable of providing assent) must be obtained before a subject can start any of the procedures at Screening (Arms 2 and 3) / Day 1 (Arm 1). The procedure(s) for obtaining written informed consent and assent of minor (if the subject is capable of providing assent) are described in [Section 13.3](#). Standard of care and local laboratory procedures performed before the signing of informed consent may be used if they occur before Screening / Day 1.

The detailed visit schedules for all study arms are presented in the subsections specified below:

1. **Arm 1 (PTPs):** Section 8.10.1
2. **Arm 2 (PUPs):** [Section 8.10.2](#)
3. **Arm 3 (PTPs):** [Section 8.10.3](#)

8.10.1 Visit schedule for Arm 1 (PTPs)

8.10.1.1 Day 1 Visit

Subjects who have participated in a previous CSL-sponsored rVIII-SingleChain study may enroll directly into Arm 1 of Study CSL627_3001. Data from the End of Study Visit from lead-in studies will be used as Day 1 parameters for this study. The following procedures will be conducted and documented at Day 1:

- Obtain written informed consent and assent of minors.
- Review of inclusion / exclusion criteria for Arm 1.
- Obtain blood sample for gene defect, if not previously obtained or gene defect not previously documented in medical records (Note: This sample should preferably be taken on Day 1. If this is not possible, the sample can be taken at any time during the study).
- Obtain blood sample for CD4 lymphocyte count (for HIV+ subjects).
- Obtain blood sample for IR.
- Record weight and height.
- Distribute eDiary and train subject on correct use.
- Assign treatment regimen (on-demand or prophylaxis).
- Distribute rVIII-SingleChain and train parents / caregivers as necessary.

The following procedures will be conducted and documented at Day 1 if not performed and documented at the previous rVIII-SingleChain study's End of Study Visit:

- Demographic information.
- Medical and surgical history.
- Hemophilia A history (previous FVIII treatment, blood group, and gene defect).
- Hemophilia A social history and activity level.
- Serum chemistry and hematology.
- Vital signs.
- Physical examination.
- Inhibitors to FVIII.

- Antibodies against rVIII-SingleChain.
- Antibodies against CHO proteins.
- Virology retention sample.
- AEs.
- Concomitant medications.

Subjects who complete all of these assessments and who fulfill the eligibility criteria for Arm 1 will be enrolled into the study. If the subject is not eligible for the study, the primary reason for screen failure must be entered in the eCRF.

8.10.1.2 Treatment Period

Subjects in Arm 1 will return to the study site every 3 months (\pm 7 days) for assessment. At each visit, the following procedures will be conducted and documented:

- Hemophilia A social history and activity level.
- Serum chemistry and hematology (until 50 EDs, then yearly).
- Vital signs (until 50 EDs, then yearly).
- Physical examination (until 50 EDs, then yearly).
- Weight.
- Height only for subjects < 18 years old.
- Incremental recovery (at the closest visits after 10 EDs, after 50 EDs, and after 100 EDs).
- Inhibitors to FVIII (at the closest visits after 10 EDs, after 50 EDs, and after 100 EDs).
- Antibodies against rVIII-SingleChain (at the closest visits after 10 EDs, after 50 EDs, and after 100 EDs).
- Antibodies against CHO proteins (at the closest visits after 10 EDs, after 50 EDs, and after 100 EDs).
- Review of subject eDiary.
- Distribution of rVIII-SingleChain.
- Record investigator assessment for treatment efficacy of any treated bleeding episodes.
- Collection of used and partially used vials of rVIII-SingleChain.
- Collection of unused vials near expiration or with insufficient shelf life to cover time duration until next visit.
- Drug accountability.
- AEs.
- Concomitant medications.

For the procedures at the End of Study Visit, see [Section 8.10.6.1](#).

8.10.2 Visit Schedule for Arm 2 (PUPs)

Summary of visit schedule for PUPs assigned to PROPHYLAXIS:

1. All PUPs assigned to prophylaxis receive their first rVIII-SingleChain dose in the clinic at Visit 1, either as a treatment dose for a bleeding episode, or as their first prophylactic dose under medical supervision.
2. At Visit 1, subjects will be provided with rVIII-SingleChain for prophylaxis therapy at home, if agreeable by the investigator.
3. After Visit 1, subjects will have monthly follow-up visits. Monthly visits continue until the subject reaches 25 EDs.
4. Once 25 EDs are reached, subjects will have 3-monthly follow-up visits until End of Study.

Summary of visit schedule for PUPs assigned to ON-DEMAND:

[figure not shown]
- All PUPs assigned to on-demand will receive their first rVIII-SingleChain dose in the clinic at Visit 1, either as a treatment dose for their first bleeding episode, or as their first exposure under medical supervision.
- Thereafter, the subject / caregiver can treat bleeding episodes with rVIII-SingleChain themselves, if agreeable by the investigator.
- Follow-up visits will occur 1 month after each rVIII-SingleChain dose. The following should be taken into consideration for scheduling these follow-up visits:
 - If the subject has a bleeding episode that spans multiple days or requires multiple doses, the follow-up visit should be scheduled based on the date of the last rVIII-SingleChain dose given for this bleeding episode.
 - If the subject has multiple rVIII-SingleChain doses within a 10-day timeframe, then the associated follow-up visits can be combined into a single visit if they occur ≤ 10 calendar days apart. In contrast, if the doses and the resulting follow-up visits occur at > 10 calendar days apart, separate follow-up visits must be performed (see example in [Figure 4](#)).
- If the interval between follow-up visits is > 1 month, monthly phone calls will be performed until the subject returns to the clinic for the next follow-up visit. These phone calls are mainly intended to collect information on bleeding status and AEs.

The timing of visits depends on the treatment assignment (ie, prophylaxis or on-demand) as well as on the clinical presentation at Screening for subjects assigned to an on-demand

regimen (ie, without or with a bleeding episode). This results in 3 different visit schedule options detailed in the following subsections and depicted in the algorithm in [Figure 3](#):

1. PUPs with or without bleeding episode at Screening and assigned to PROPHYLAXIS:
[Section 8.10.2.1](#)
2. PUPs WITHOUT bleeding episode at Screening and assigned to ON-DEMAND:
[Section 8.10.2.2](#)
3. PUPs WITH bleeding episode at Screening and assigned to ON-DEMAND:
[Section 8.10.2.3](#)

Figure 3: Algorithm for treatment assignment and visit structure in Arm 2 PUPs

Abbreviations: ED = exposure day; EOS = End of Study; INH = inhibitor; N = no; PUP = previously untreated patient; Y = yes.

Figure 4: Example of visit structure for PUPs assigned to on-demand treatment

Follow-up visits scheduled to occur within 10 days of one another may be combined into one follow-up visit. Combinations are at the Investigator's discretion. Below is an example of possible combinations of follow-up visits.

- Visit 2 is the follow-up visit for the first rVIII-SingleChain dose at Screening/Visit 1
- Visit 3 is the combined follow-up visit for rVIII-SingleChain doses 2 and 3.
- Visit 4 is the combined follow-up visit for rVIII-SingleChain doses 4 and 5.
- Due to the timing of rVIII-SingleChain doses, additional combinations of follow-up visits are possible.

Abbreviations: PUP = previously untreated patient

8.10.2.1 Visit Schedule for Arm 2 PUPs With or Without Bleeding Episode at Screening and Assigned to PROPHYLAXIS

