3.2.1 Prophylaxis Treatment Regimen

In previous studies, most subjects received prophylaxis treatment with an initial range of 15 to 50 IU/kg rVIII-SingleChain every second day or 2 to 3 times per week. In all study arms, the dose prescribed will be based on the subject's weight at the most recent visit. All subjects will be dosed according to the actual potency printed on the vial label and will be treated by IV injection.

- In Arms 1 and 3 (PTPs), the investigator will determine the rVIII-SingleChain dose and dosing schedule for the subject based upon the subject's PK profile, rVIII-SingleChain

PK data, previous FVIII treatment regimen, bleeding phenotype (if available), and taking into consideration the WFH guidelines [WFH, 2012].

- In **Arm 2 (PUPs)**, the investigator will determine the rVIII-SingleChain dose and dosing schedule at their discretion, taking into consideration the WFH guidelines [WFH, 2012], subject's age and other disease characteristics (eg, bleeding phenotype).

3.2.2 Treatment of Bleeding Episodes in Subjects on Prophylaxis and in Subjects On-Demand Treatment Regimens

In the event of a bleeding episode, subjects will be treated at a dose pre-determined by the investigator based on the type and severity of the bleeding episode. All subjects should treat bleeding episodes with rVIII-SingleChain when they occur, regardless of the assigned treatment regimen. The desired FVIII level for the treatment of a bleeding episode (on-demand treatment) is based on the recommendations of the WFH [WFH, 2012].

All subjects will be dosed according to the actual potency printed on the vial label and will be treated by IV injection.

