8.10.2.2.3 Treatment Period

8.10.2.2.3.1 Follow-up Visits After Each rVIII-SingleChain Dose

While on an on-demand regimen, subjects will have follow-up visits **1 month (± 7 days) after each rVIII-SingleChain dose**, until End of Study.

The following procedures will be conducted and documented at each follow-up visit:

- Obtain blood sample for inhibitors to FVIII.
- Obtain blood sample for antibodies against rVIII-SingleChain and CHO proteins.
- Obtain blood sample for serum chemistry and hematology.
- Hemophilia A social history and activity level.
- Vital signs.
- Physical examination.
- Record weight and height.
- Review of subject eDiary.
- Record investigator assessment for treatment efficacy of any bleeding episodes treated at home.
- If rVIII-SingleChain administered at the clinic: record investigator assessment of local tolerability.
- Collection of used and partially used vials of rVIII-SingleChain.
- Collection of unused vials near expiration or with insufficient shelf life to cover time duration until next visit.
- Perform drug accountability.
- Distribute rVIII-SingleChain and train parents / caregivers as necessary.
- Review AEs.
- Review concomitant medications.
- If treatment regimen is changed, instruct the subject and parent / caregiver on the change in visit schedule and update the eCRF (see [Section 3.2.5](#)).

For the procedures at the End of Study Visit, see [Section 8.10.6.2](#).

8.10.2.2.3.2 Monthly Telephone Calls

Subjects who do not experience a bleeding episode requiring treatment with rVIII-SingleChain within 1 month after the preceding visit will have monthly telephone calls (time window: ± 7 days) until the next bleeding episode / rVIII-SingleChain dose occurs. The following assessments will be performed at each monthly telephone call:

- Record date of telephone contact.
- Record name of staff member who contacted the subject.
- Confirm that no bleeding episodes have occurred since last visit.
- Review eDiary entries with subject.
- Review AEs.
- Review concomitant medications.
- Record data from telephone contact in eCRF.
- Arrange unscheduled visit if needed.

8.10.2.3 Visit Schedule for Arm 2 PUPs WITH Bleeding Episode at Screening and Assigned to ON-DEMAND

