11.2.3 Efficacy Population

The efficacy population will consist of all subjects in the safety population who receive at least 1 dose of rVIII-SingleChain as part of either routine prophylaxis treatment or on-demand treatment during the study. Additionally, the efficacy population will only include subjects who do not have an inhibitor.

The Efficacy population might be the same as the Safety population.

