#### 3.5.3 Efficacy Population

The Efficacy population will consist of all subjects in the Safety population who received at least 1 dose of rVIII-SingleChain for either routine prophylaxis treatment or on-demand treatment during the study.

The Efficacy population might be the same as the Safety population. In this case, analyses will not be repeated for both the populations.

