## 4.6 Efficacy Analysis

The efficacy endpoints will be summarized and analyzed for the Efficacy population unless otherwise specified. The surgery substudy efficacy data will be summarized for the Surgery population. Efficacy analyses will be performed separately for the PTPs and PUPs and by modality. Efficacy results for the PUPs will be presented by inhibitor status (positive, negative) and overall.

The efficacy evaluation period begins on Treatment Day 1 date in this study and ends at the End of study Visit in this study or the last date of dose, whichever occurs later. Only those treated bleeding episodes and doses which fall within the efficacy evaluation period will count

towards the efficacy evaluation. The summary statistics to be presented are described in [Section 4.1](#).

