### AsBR

AsBR will be derived by inhibitor status and overall as follows:

$$(\text{number of bleeding events}) / (\text{observed treatment period of interest days}) * 365.25.$$

Only bleeding events requiring treatment will be included in the derivation of bleeding rates. The AsBR will be estimated for subjects who complete at least 8 weeks of treatment on the given inhibitor status using the subject's observed data. If the subject does not complete at least 8 weeks of treatment on the given inhibitor status, then the AsBR will be considered missing.

The number of spontaneous bleeding episodes per year based on a Poisson model and associated 95% CI and the number and percentage of subjects with zero bleeding episodes will be presented. In addition, the rate ratio of Prophylaxis modality to On-Demand modality (Prophylaxis- On-Demand) will be presented, along with the associated 95% CI, as obtained by the Poisson model.

Spontaneous bleeding episodes are those classified as 'Non-traumatic' in e-Diary or 'Spontaneous' in the eCRF. Annualized spontaneous bleeding rate will also be summarized for the following subgroup:

- Positive non-inhibitory Anti-Drug Antibodies (ADAs) and negative during the study
- Age based on age in this study: for PTPs: 0 to < 6 years,  $\geq 6$  to < 12 years,  $\geq 12$  to < 18 years and  $\geq 18$  to  $\leq 65$  years, 0 to <12 years,  $\geq 12$  to  $\leq 65$  years.
- Prophylaxis frequency: every second day, 3 times per week, 2 times per week, other regimen.

In these subgroup analyses rate ratio of Prophylaxis modality to On-Demand modality won't be displayed.

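### The Efficacy population is defined by the purpose of a dose and does not say whether an on-demand PUP's supervised first-exposure dose qualifies; read literally, on-demand boys with no treated bleed fall out of AsBR

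*Protocol*

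**What the plan says.** Four parts of the plan bear on this point.

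- **First dose.** Protocol 8.10.2 has every on-demand PUP receive his first dose at Visit 1, "either as a treatment dose for their first bleeding episode, or as their first exposure under medical supervision". For a prophylaxis PUP without a bleed, the same section calls the Visit 1 dose his first prophylactic dose.
- **Population.** SAP 3.5.3 admits Safety-population subjects who "received at least 1 dose of rVIII-SingleChain for either routine prophylaxis treatment or on-demand treatment during the study". Protocol 11.2.3 has the same condition, "at least 1 dose of rVIII-SingleChain as part of either routine prophylaxis treatment or on-demand treatment during the study", and adds an inhibitor exclusion that the SAP removes and declares in 4.11. Both sections add that the Efficacy and Safety populations might be the same.
- **Analysis.** SAP 4.6 states: "The efficacy endpoints will be summarized and analyzed for the Efficacy population unless otherwise specified". The AsBR text under SAP 4.6.1.1 counts only bleeds that required treatment. It sets AsBR to missing for less than 8 weeks on the given inhibitor status, and plans a prophylaxis/on-demand rate ratio from a Poisson model. It also says that "the number and percentage of subjects with zero bleeding episodes will be presented".
- **Bleed-free time is observed.** Protocol 8.10.2.2.3 schedules monthly calls for on-demand boys who do not bleed, with the task "Confirm that no bleeding episodes have occurred since last visit".

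**The concern.** Entry to the analysis set depends on why a dose was given. A prophylaxis boy meets the condition with his first scheduled dose, whether or not he ever bleeds. An on-demand boy who enters without a bleed may have nothing but the supervised dose until he treats a bleed. If that dose does not count, his entry depends on having had a treated bleed, while his observed bleed-free time is discarded.

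This would be selection on the outcome in one regimen only. The subjects removed all have zero treated bleeds, so removing them can move the on-demand AsBR in one direction only, upward. The planned rate ratio would move toward prophylaxis. The reported share of on-demand subjects with zero bleeds would also be too low.

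**Working it through.** **1. Does the first-exposure dose qualify?** Neither document says so directly. The wording that bears on it:

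- Protocol 3.2.2 equates the two terms in a parenthesis: "treatment of a bleeding episode (on-demand treatment) is based on".
- Protocol 11.2.2 lists routine prophylaxis and on-demand treatment as examples of reasons for a dose, alongside surgery. Protocol 8.3.1 lists on-demand as a type of treatment.
- Protocol 8.10.2 sets the supervised exposure apart from a treatment dose.
- The Visit 1 list for on-demand boys with a bleed (8.10.2.3.2) includes an investigator efficacy rating. The list for those without a bleed (8.10.2.2.2) does not.
- The infusion reasons in SAP 4.6.2.3 are routine prophylaxis, bleeding event, surgery, post-surgery, prevention before activity and additional treatment. None is a first exposure.

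The literal reading is therefore that the dose does not qualify. It is a reading, not an express rule.

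**2. Who would be left out?** Only a boy assigned to on-demand with no treated bleed of any cause and no prophylaxis dose. A boy with one treated traumatic bleed is in, with AsBR 0. So is a boy who switches and receives a prophylaxis dose.

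**3. How likely is such a boy?** The plan gives no bleed rate, so the rates here are assumed. With a constant rate r of treated bleeds per year, P(no treated bleed in T years) = exp(−rT):

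| r per year | 8 weeks | 1 year | 2 years | 6 years |
|---|---|---|---|---|
| 1 | 0.86 | 0.37 | 0.14 | 0.002 |
| 2 | 0.74 | 0.14 | 0.02 | <0.001 |
| 5 | 0.46 | 0.007 | <0.001 | <0.001 |

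Inhibitor-negative PUPs stay until 75 EDs, expected to take up to 6 years (Protocol 3.3). Zero treated bleeds is therefore plausible mainly for early leavers and short on-demand periods.

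**4. What does dropping one such boy do?** The plan states no AsBR and no number of on-demand boys, so there is no figure to reproduce. Let n be the assumed number of on-demand boys and k the number dropped.

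- *Mean of subject-level AsBR* is multiplied by n/(n−k). With k = 1: 6/5 = 1.20, 12/11 = 1.091, 24/23 = 1.043. The mean is unweighted, so this holds for any dropped boy past the 8-week threshold, however short his time.
- *Pooled Poisson rate* is multiplied by (time including him)/(time excluding him). With 2 years for each remaining boy and t years for the dropped boy, the factor is [2(n−1) + t]/[2(n−1)]:

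| n | t = 8 weeks (0.153 y) | t = 1 year | t = 2 years |
|---|---|---|---|
| 6 | 10.153/10 = 1.015 | 11/10 = 1.10 | 12/10 = 1.20 |
| 12 | 22.153/22 = 1.007 | 23/22 = 1.045 | 24/22 = 1.091 |

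With k = 2 and equal follow-up the factors are 6/4 = 1.50, 12/10 = 1.20 and 24/22 = 1.091. With k = 0 the factor is 1.00.

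**The case against.** The strongest case on the other side is that no sentence excludes the Visit 1 dose. Protocol 11.2.3 asks for a dose given as part of on-demand treatment. Elsewhere on-demand names the assigned regimen (Protocol 3.2, 6.2.1), and under that regimen the Visit 1 dose triggers the first follow-up visit. Both documents allow that the Efficacy and Safety populations may coincide. The AsBR text makes the rate missing only for short time, never for zero bleeds, and plans a count of zero-bleed subjects. How the dose is recorded depends on the eCRF; if it is entered as routine prophylaxis, the boy is in. Regimen is chosen by the investigator and no p-values are planned, so the rate ratio is descriptive in any case.

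Much of this stands, and it is why the point is conditional. It does not settle how the dose is classified. The expectation that the populations may coincide is not a rule, and the plan to report zero-bleed subjects shows that the population wording can work against the intended analysis.

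A reader might infer more than the documents support:

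- *That no on-demand subject can appear with zero treated bleeds.* Regimen switches are allowed (Protocol 3.2.5), so a boy with any prophylaxis dose is in the population and may have a bleed-free on-demand period.
- *That on-demand boys enter only once they have had the primary outcome.* The outcome is spontaneous bleeds; a treated bleed of any cause gives entry.
- *That the inflation is large.* The factor 1/(1−P0), where P0 is the share with no treated bleed, gives 1.58 at 2 treated bleeds a year over 6 months, but only if every boy has that short follow-up. At 2 years it is 1.019. The plan supplies neither rates nor on-demand counts.
- *That PTPs on on-demand are affected in the same way.* They have no primary efficacy endpoint, and SAP 4.6.2.1 already makes a PTP's regimen-specific ABR missing when he has no treated bleed on that regimen. Membership does not change that subject-level rate.

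**Conclusion.** The concern holds in conditional form. The population definition leaves the first-exposure dose unclassified. On the better-supported literal reading, AsBR membership for some on-demand PUPs depends on having had a treated bleed. The direction is certain if any such boy is dropped: the on-demand AsBR rises and the rate ratio moves toward prophylaxis.

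The size cannot be derived from the documents. With 6 or 12 on-demand boys (assumed), dropping one raises the rate by between about 1% (pooled Poisson, 8 weeks for him against 2 years for the others) and 20% (6 boys, unweighted mean or equal follow-up). If no such boy exists, or if the dose is treated as qualifying, the effect is zero. Arm 2 targets 24 PUPs across both regimens, so a single boy can be visible in the result.

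The explicit zero-bleed rule in SAP 4.6.2.1 is a clearer form of the same problem. Its paragraph opens with PTP rates, and its reach for PUP ABR is not stated.

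**What to change.** 1. In SAP 3.5.3, define the Efficacy population as all Safety-population subjects assigned to a prophylaxis or on-demand regimen who received at least one dose of rVIII-SingleChain for any reason.
2. In the AsBR text, state that subjects with no treated bleed contribute zero bleeds and their full time on regimen, subject to the 8-week rule.
3. In SAP 4.6.2.1, delete the clause that makes ABR missing for a subject with no treated bleed on the regimen. Keep the 8-week condition.
4. Declare all of this in SAP 4.11, next to the change already declared there for the Efficacy population.

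The cost is one or two sentences in the SAP. The downside is a slightly lower on-demand rate if such subjects exist. Per-bleed success rates do not change, because these subjects have no treated bleed to rate. PTP results have already been analysed (SAP 4.1.2), so any PTP rate recomputed under item 3 should be labelled as a change made after that analysis.
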